## **EMA Analyses**

### **Co-primary Analysis of Change from Baseline in the MoCA Total Score at 12 Weeks for EMA registration**

The change from baseline of MoCA total score for E2027 dose compared to placebo will be analyzed using the approach proposed by Mehrotra et al (2017) with slight modification based on reasons for missing data. The following is a list of the missing reasons and their missing mechanisms:

Data not observed because of dropouts (primary reason) due to AEs, lack of efficacy or any other intercurrent events related to treatment or study outcome will be considered as missing not at random (MNAR). Where there are other/secondary reasons for dropout that relate to a new drug being taken in response to an AE, this will also be counted as MNAR, even if the primary reasons for drop out may not be classed as not related to treatment or outcome. Where data are not done with the patient continuing study, the data will be considered MNAR where reasons for missingness are related to AEs, the subject is sleepy/drowsy, the subject is delirious, or the subject refused/declined (where refusal was not related to withdrawal of consent).

Data not observed because of dropouts due to intercurrent events definitely not related to treatment or outcome (eg, withdraw consent due to logistical problems) will be considered as missing at random (MAR). Where data are not done with the patient continuing study, the data will be considered MAR where reasons for missingness are not related to AEs, the

subject is sleepy/drowsy, the subject is delirious, or the subject refused/declined, except if the refusal was due to withdrawal of consent.

The missing endpoint values considered as MAR can be imputed using condition distribution from the observed endpoint values and therefore can be handled by MMRM analysis assuming MAR. The mean of missing endpoint values in the E2027 treatment group considered as MAR can be viewed as implicitly imputed using the estimated means of endpoint values of completers and all subjects through MMRM analysis including completers and subjects with missing values considered as MAR in the E2027 treatment group. The mean of missing endpoint values in E2027 treatment group considered as MNAR will be imputed by the mean of the overall endpoint distribution under placebo as described next. The mean of the overall endpoint distribution under placebo will be obtained using mixed effects model of repeated measures (MMRM) within placebo group assuming MAR. Test statistics and the p-value will be obtained as described by Mehrotra, et al. (2017). In the presence of subjects with missing endpoint values considered as MAR, the superscript of “drop” refers to “subjects with missing endpoint values considered as MNAR” and the superscript of “comp” refers to “completers and subjects with missing endpoint values considered as MAR”.

### **Sensitivity Analysis of Change from Baseline in the MoCA Total Score at 12 Weeks for EMA registration**

A sensitivity analysis will be produced to repeat the primary analysis for MoCA but to censor data after changes in AChEI medications. For this the following missing mechanism will be added to the above reasons in the primary analysis

The effect had rescue medication not been made available to subjects prior to week 12 is not observable for subjects who initiated prohibited or restricted rescue medication. For these subjects, the data collected after initiation of prohibited rescue medication are assumed to contain no treatment effect in the E2027 treatment group. Technically, response data collected after initiation of new AChEIs or after any change in concomitant AChEIs stable dose will be treated as MNAR such that response data treated as MNAR in the E2027 treatment group would be imputed by the mean response in the placebo treatment group as described by the imputation method below.

In order to generate inputs for proposed primary and sensitivity analyses for the EMA registration, a MMRM will be used in separate MMRM analyses for each treatment group for all randomized subjects as well as completers assuming MAR for both treatment groups. The model will be adjusted for baseline MoCA, visit (Week 6 and Week 12), randomization stratification variables (receiving AChEI or not, geographical region [North America, Europe, Japan]), and baseline MoCA  $\times$  visit as fixed effects. An unstructured covariance matrix will be used to model the covariance of within subject effect; if MMRM fails to converge then a covariance structure with fewer parameters from the following list will be employed according to the prespecified order in the list until the MMRM converges. The list of covariance structure will include Heterogeneous Toeplitz, Toeplitz, Heterogeneous

Compound Symmetry, and Compound Symmetry. The Kenward-Roger approximation will be used to estimate the denominator degrees of freedom when unstructured covariance matrix is used. If MMRM fails to converge and a structured covariance matrix is used, the empirical method will be used to compute variance-covariance matrix of the fixed-effects parameters (sandwich estimator). The values of baseline MoCA will be adjusted using the overall baseline mean of all study subjects in computing least square (LS)-means.

### **Co-primary Analysis of the CIBIC-Plus Scale at 12 Weeks for EMA registration**

The primary analysis of the CIBIC-Plus scale at 12 weeks will be based on control-based pattern imputation at subject level (Yang, 2014). The CIBIC-Plus scale at 12 weeks will be imputed as an ordinal response variable. The same missing reasons and corresponding missing mechanism as in the analysis of change from baseline in MoCA total score will be used in this analysis. Only the missing ordinal responses in E2027 treatment group considered as MNAR will be imputed by ordinal responses observed in the placebo group using a pattern-mixture model approach under MNAR assumption. Other missing ordinal responses will be imputed assuming MAR. This can be implemented using multiple imputation in two steps: Step 1: impute E2027 dropouts considered as MAR and placebo dropouts using multiple imputations assuming MAR, e.g., generate N (N = 100 or larger) datasets; Step 2: impute the E2027 dropouts considered as MNAR using placebo data and a pattern-mixture approach under the MNAR assumption for each above imputed dataset in Step 1. In each step, the multiple imputations will be conducted using Proc MI implemented in SAS 9.4. The logistic regression method of classification variables will be specified to impute missing values for CIBIC-Plus scale. In Step 2, an additional MNAR statement will be used to complete the control-based pattern imputation at subject level.

The CIBIC-Plus scale at 12 weeks (observed or imputed) will be analyzed using the proportional odds model, a special case of generalized linear mixed models (GLMM), in multiply imputed data sets. The results obtained from all multiply imputed data sets will be combined for overall inference using Rubin's rules. The GLMM model will include treatment, randomization stratification variables (receiving AChEI or not, geographical region [North America, Europe, Japan]) as fixed effects. The model will be fitted using GLMM with a multinomial distribution and a cumulative logit link function. The proportional odds ratio estimate between E2027 and placebo, the corresponding 95% CI and P-values will be presented.

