9.5.1.3.2 CLINICIAN'S INTERVIEW BASED IMPRESSION OF CHANGE PLUS CAREGIVER INPUT (CIBIC-PLUS)

The CIBIC-Plus scale is designed to measure various domains that describe subject function: general, mental/cognitive state, behavior, and activities of daily living. It is a semi-structured global rating derived from a comprehensive interview with the subject and caregiver or informant by an independent rater who has no access to the source data or other psychometric test scores conducted postrandomization as part of the given protocol.

At Baseline (Visit 2), this independent rater will use a related tool, the CIBIS-Plus. This scale, which assesses disease severity on a 7-point scale from 1 = normal to 7 = extremely ill, establishes a point of reference for subsequent interviews using the CIBIC-Plus.

During the Treatment Period, the rater will administer the CIBIC-Plus separately to the subject and the caregiver or informant as designated in [Table 6](#). At the end of each pair of interviews during each of these study visits, the rater alone will determine separately for each of the 4 domains whether the disease has improved, worsened, or remained unchanged since the evaluation at Baseline. The CIBIC-Plus scores are: 1 (marked improvement), 2 (moderate improvement), 3 (minimal improvement), 4 (no change), 5 (minimal worsening), 6 (moderate worsening) and 7 (marked worsening).

The CIBIC-Plus will also be assessed at ED and Unscheduled Visits.

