mechanism (ie, all missing data will be considered as MNAR regardless of reason of dropouts), will be provided.

If the proportional odds assumption is contradicted by the observed data in either entire population or any stratum, the GLMM method will be replaced by the non-parametric van Elteren test in both primary analysis and sensitivity analysis. The CIBIC-Plus scale at 12 weeks will be analysed using van Elteren test adjusting 2 randomization stratification variables (receiving AChEI or not; geographical region [North America, Europe, Japan]). The null hypothesis corresponding to the van Elteren test is that there is no difference in the location of distribution of CIBIC-Plus scale at 12 weeks between E2027 and placebo. The corresponding alternative hypothesis is that there is a difference in the location of distribution of CIBIC-Plus scale at 12 weeks between E2027 and placebo.

The potential effect of baseline MMSE on the primary result will be evaluated as an additional covariate in the primary model as appropriate. Subgroup (eg, region, age group, baseline AChEI status, baseline MMSE group, and baseline memantine status) analyses will be performed as appropriate. (revised per Amendment 03)

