### 5.3.2 Adjustments for Covariates of Interest

The baseline value will be used as a covariate, and stratification variables (on AChEI or not and geographical region (US, Europe, Japan)) will be used as factors in the efficacy models

for analysis of continuous endpoints. Baseline for the primary and secondary efficacy endpoints is defined as the last pre-treatment assessment.

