### **Co-primary Analysis of the CIBIC-Plus Scale at 12 Weeks for non-EMA registration**

CIBIC-Plus scale at 12 weeks will be analyzed using GLMM. The GLMM model will include treatment, visit, randomization stratification variables (receiving AChEI or not, geographical region [North America, Europe, Japan]), and treatment x visit as fixed effects. The model will be fitted using GLMM with a multinomial distribution and a cumulative logit link function. If the proportional odds assumption is contradicted ( $p < 0.05$  in Score Test for the Proportional Odds Assumption) by the observed data in either the entire population or any stratum, the GLMM method will be replaced by the nonparametric van Elteren test adjusting 2 randomization stratification variables (on stabilized AChEI dose or not; geographical region [North America, Europe, Japan]).

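### The CIBIC-Plus and CGIC-DLB models carry no baseline clinical score, and the protocol's baseline-MMSE covariate check is missing from the SAP; adding baseline CIBIS-Plus would be a cheap, modest efficiency gain

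*SAP*

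**What the plan says.** SAP 5.4.1 gives two CIBIC-Plus co-primary models. For EMA: "The GLMM model will include treatment, randomization stratification variables (receiving AChEI or not, geographical region [North America, Europe, Japan]) as fixed effects". For non-EMA: "The GLMM model will include treatment, visit, randomization stratification variables (receiving AChEI or not, geographical region", followed by the treatment-by-visit term. SAP 5.4.2 has CGIC-DLB analysed in the same way as CIBIC-Plus.

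The difference from MoCA follows from SAP 5.3.2. It begins "The baseline value will be used as a covariate, and stratification variables", and the rest of that sentence confines the rule to models for continuous endpoints. The MoCA models accordingly include baseline MoCA; for EMA, "The model will be adjusted for baseline MoCA, visit (Week 6 and Week 12".

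Baseline scores are available. Protocol 9.5.1.3.2 says "At Baseline (Visit 2), this independent rater will use a related tool, the CIBIS-Plus", and that this scale "establishes a point of reference for subsequent interviews using the CIBIC-Plus". Protocol Table 6 schedules MoCA at Screening and Baseline and MMSE at Screening. SAP 5.2.4 already summarises all three by arm.

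Protocol 9.7.1.6.1 also says: "The potential effect of baseline MMSE on the primary result will be evaluated as an additional covariate in the primary model as appropriate". In SAP 5.4.1 and Table 4, MMSE appears only as a subgroup. SAP Section 7 (changes in the planned analyses) does not mention the covariate evaluation. The Version 4 change table says supplementary analyses were reduced but does not name this one.

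**The concern.** One co-primary is adjusted for baseline and the other is not, and the SAP gives no reason beyond the type of endpoint. Success needs both co-primaries, so any power left unused on CIBIC-Plus counts against the trial. If baseline severity predicts the change rating, a score already in the database could recover some of that power and account for chance imbalance between arms.

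Separately, an evaluation announced in the protocol has disappeared without record. A reader of the study report could not tell whether it was dropped deliberately or overlooked.

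**Working it through.** **Inputs from the SAP** (Sections 4 and 5): 80 completers per arm; MoCA difference 0.6, SD 1.3; CIBIC-Plus odds ratio 2.607; about 80% power on both endpoints; two-sided 5%.

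**Assumptions, not in the documents:** placebo proportions over CIBIC-Plus scores 1 to 7 of 2, 8, 20, 30, 25, 10 and 5% (mid-spread); a correlation r between baseline severity and the latent rating; independent endpoints unless stated.

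**1. The plan's own figure**
- Dropout: 80/(1 - 0.12) = 90.9, so 91 per arm, as stated.
- MoCA: z = 0.6/(1.3 x sqrt(2/80)) = 2.92; power = Phi(2.92 - 1.96) = 0.831.
- CIBIC-Plus (Whitehead): V = (160/12) x (1 - sum of p^3), where p is the category proportion averaged over arms. The bracket is 0.951, so V = 12.68. Then z = ln(2.607) x sqrt(12.68) = 0.958 x 3.561 = 3.41, and power = Phi(3.41 - 1.96) = 0.927.
- Joint power: 0.831 x 0.927 = 0.77 under independence; 0.783 and 0.794 if the endpoints correlate 0.3 and 0.5.

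The stated 80% can be neither confirmed nor refuted, because the SAP gives neither the category distribution nor the correlation between endpoints.

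**2. Adding a baseline covariate**

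Approximation: z is divided by sqrt(1 - r^2).

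| r | z | CIBIC-Plus power | Joint power |
|---|---|---|---|
| 0 | 3.41 | 0.927 | 0.77 |
| 0.2 | 3.48 | 0.936 | 0.778 |
| 0.3 | 3.58 | 0.947 | 0.787 |
| 0.4 | 3.72 | 0.961 | 0.799 |

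**3. Other placebo distributions** (r = 0, then r = 0.2 to 0.4)
- Half of placebo scoring no change: CIBIC-Plus 0.905, then 0.916 to 0.946; joint 0.752, then 0.761 to 0.786.
- Flat: CIBIC-Plus 0.932, then 0.941 to 0.965; joint 0.775, then 0.782 to 0.802.
- 70% scoring no change: CIBIC-Plus 0.823, then 0.838 to 0.883; joint 0.684, then 0.697 to 0.734.

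**4. Where the gain comes from**

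Proportional-odds fits were simulated, 1000 runs per r, with a Monte Carlo error of about 0.8 points.
- At r = 0.3 the SD of the log odds ratio was 0.282 unadjusted and 0.283 adjusted, while its mean moved from 0.97 to 1.04.
- At r = 0.5 the SD rose from 0.298 to 0.318 and the mean moved from 0.97 to 1.16.
- Adjusted power was 0.935, 0.962 and 0.964 at r = 0.2, 0.3 and 0.4. This is within about two Monte Carlo errors of the table.

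**5. Ceiling**

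Joint power cannot exceed MoCA power, 0.831. With the SAP's revised pair (difference 1.4, SD 3), z = 1.4/(3 x sqrt(2/80)) = 2.95 and MoCA power is 0.839, so the ceiling hardly moves.

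**The case against.** The strongest case is that the contrast with MoCA is principled. CIBIC-Plus is itself a rating of change since Baseline, so it has no baseline value of its own, and its correlation with baseline severity may be small. That stands: the gain may be close to nil, and the documents give no correlation.

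A second objection is that adjustment changes the quantity estimated. That is true, but the planned odds ratio is already conditional on AChEI use and region, and under no treatment effect the conditional and unadjusted odds ratios are both 1, so the null hypothesis is unaffected.

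A third is the van Elteren fallback, which uses only the two stratification factors. If it is triggered, the adjustment has no effect. The trigger is p < 0.05 overall or in any stratum. If that means seven tests (six strata plus the whole population), and they were independent, the chance under true proportional odds would be 1 - 0.95^7 = 0.30. This is only a rough guide, since the overall test overlaps the stratum tests.

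Four stronger readings are tempting, and the documents do not support them:
- That the unadjusted analysis is biased or invalid. Chance imbalance under randomization does not invalidate the test.
- That precision is being given away free. Step 4 shows no narrowing of the log odds ratio.
- That the SAP contradicts the protocol's primary model. The protocol sentence describes an additional evaluation where appropriate; only its silent disappearance is a gap.
- That baseline was deliberately left out of the CIBIC-Plus imputation model. The SAP names no predictors for Proc MI at all, which is a general gap in specification.

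**Conclusion.** The point holds as an efficiency improvement of low severity, together with an unrecorded departure from the protocol. Neither CIBIC-Plus co-primary model, nor the CGIC-DLB models that follow them, uses a baseline clinical score. The baseline-MMSE evaluation is missing from SAP 5.4.1, Table 4 and Section 7.

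In the mid-spread case, r of 0.2 to 0.4 is worth about 1 to 3 points of CIBIC-Plus power and a similar amount of joint power. The gain is larger only if placebo ratings cluster heavily on no change, and it is nil at r = 0. The size rests entirely on the assumed correlation, category distribution and independence. The missing MMSE evaluation does not depend on any of these.

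**What to change.** Before unblinding:

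1. Prespecify one covariate, the baseline CIBIS-Plus score, in the CIBIC-Plus and CGIC-DLB models for both registrations. State its coding; a linear term on the 7-point score costs one degree of freedom.
2. Include it in the Proc MI model for missing CIBIC-Plus, and list that model's other predictors.
3. State that the odds ratio is conditional on baseline severity as well as on the strata. Keep the current model as supplementary.
4. State that the van Elteren fallback remains stratified by AChEI use and region only.
5. Restore the baseline-MMSE covariate analysis as supplementary, or record its removal in SAP Section 7.

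If evidence is wanted first, the correlation can be estimated from pooled blinded data, which the sponsor has already used to revise the MoCA assumptions.

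The cost is SAP wording, with no new data. Because SAP Section 7 ties the primary analyses to FDA correspondence and EMA advice, the change may also need to be communicated to both agencies. The downsides are an odds ratio conditional on baseline severity, and one degree of freedom lost if the score turns out not to be prognostic.

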### **Sensitivity Analysis of the CIBIC-Plus Scale at 12 Weeks for EMA registration**

A sensitivity analysis will be produced to repeat the primary analysis for CIBIC-Plus but to censor data after changes in both AChEI and non-AChEI medications. For this the following missing mechanism will be added to the above reasons in the primary analysis

The effect had rescue medication not been made available to subjects prior to week 12 is not observable for subjects who initiated prohibited or restricted rescue medication. For these subjects, the data collected after initiation of prohibited rescue medication are assumed to contain no treatment effect in the E2027 treatment group. Technically, response data collected after initiation of new AChEIs or non-AChEIs prohibited or restricted medications (as specified in Concomitant Drug/Therapy section in the protocol) or after any change in concomitant AChEIs or non-AChEIs stable dose will be treated as MNAR such that response data treated as MNAR in the E2027 treatment group would be imputed by the mean response in the placebo treatment group as described by the imputation method below.

A sensitivity analysis that excludes all subjects with changes in AChEI or non-AChEI restricted medications will also be performed.

If the proportional odds assumption is contradicted ( $p < 0.05$  in Score Test for the Proportional Odds Assumption) by the observed data in either the entire population or any stratum, the GLMM method will be replaced by the nonparametric van Elteren test in both primary analysis and sensitivity analysis. The CIBIC-Plus scale at 12 weeks will be analyzed using van Elteren test adjusting 2 randomization stratification variables (on stabilized AChEI dose or not; geographical region [North America, Europe, Japan]). The H0 corresponding to the van Elteren test is that there is no difference in the location of distribution of the CIBIC-Plus scale at 12 weeks between E2027 and placebo. The corresponding alternative hypothesis is that there is a difference in the location of distribution of the CIBIC-Plus scale at 12 weeks between E2027 and placebo.

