### Clinician's Interview Based Impression of Change Plus Caregiver Input (CIBIC-Plus)

This scale is designed to measure various domains that describe subject function: general, mental/cognitive state, behavior, and activities of daily living. The CIBIC-Plus scores will be assigned by clinicians and the possible scores are: 1 (marked improvement), 2 (moderate improvement), 3 (minimal improvement), 4 (no change), 5 (minimal worsening), 6 (moderate worsening) and 7 (marked worsening).

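### The EMA medication-change sensitivity analysis of CIBIC-Plus carries over the MoCA mean-imputation sentence, which contradicts the ordinal imputation it is meant to repeat

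*SAP*

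**What the plan says.** The EMA section of SAP 5.4.1 plans a sensitivity analysis to "repeat the primary analysis for CIBIC-Plus but to censor data after changes in both AChEI and non-AChEI medications". It states that "the following missing mechanism will be added to the above reasons in the primary analysis": data after a change in AChEI or non-AChEI medication become missing not at random (MNAR). It then adds that such data in the E2027 arm "would be imputed by the mean response in the placebo treatment group as described by the imputation method below". What comes after this in the section is an analysis excluding subjects with medication changes, and the van Elteren fallback. Neither is an imputation method.

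The analysis to be repeated handles MNAR scores differently. Under the EMA co-primary analysis of CIBIC-Plus, "The CIBIC-Plus scale at 12 weeks will be imputed as an ordinal response variable", and "Only the missing ordinal responses in E2027 treatment group considered as MNAR will be imputed by ordinal responses observed in the placebo group". The tool is named: "The logistic regression method of classification variables will be specified to impute missing values for CIBIC-Plus scale", with an MNAR statement in Step 2, at least 100 data sets and Rubin's rules. SAP 5.3.5.1 gives the same subject-level, control-based rule for EMA CIBIC-Plus.

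SAP 8.3 defines the scale as seven whole-number scores, beginning "1 (marked improvement), 2 (moderate improvement), 3 (minimal improvement), 4 (no change") and ending at 7 for marked worsening.

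**The concern.** A placebo mean is in general not one of the seven CIBIC-Plus categories. Mean imputation fits the EMA analysis of MoCA, which works with arm means. It does not fit a cumulative-logit model for an ordinal score.

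The sentence is also the only rule written specifically for CIBIC-Plus data censored at a medication change. A programmer could therefore draw ordinal categories, enter the unrounded mean, or enter the rounded mean, and the SAP does not say which instruction takes precedence.

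At stake is how this analysis can be interpreted. The protocol (9.7.1.6.1) defines the effect of interest as the one without initiation or dose change of prohibited or restricted medication. SAP section 7 moved that censoring out of the co-primary analyses. For EMA CIBIC-Plus, this analysis and the exclusion analysis are the two that still address it. If the imputation rule changes together with the censoring, a difference from the primary result cannot be attributed to the censoring.

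**Working it through.** The plan gives no figure to reproduce on this point. The check has two parts.

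**1. The texts side by side**

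| Place | Rule for MNAR E2027 data |
|---|---|
| SAP 5.3.5.1, EMA CIBIC-Plus | Control-based pattern imputation at subject level |
| SAP 5.4.1, EMA co-primary CIBIC-Plus | Ordinal categories taken from placebo, Step 2 |
| SAP 5.4.1, EMA MoCA sensitivity | Placebo mean; the MMRM inputs follow |
| SAP 5.4.1, EMA CIBIC-Plus sensitivity, opening | Repeat the primary analysis with one more missing-data reason |
| SAP 5.4.1, EMA CIBIC-Plus sensitivity, later sentence | Placebo mean; no method follows |

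The last row conflicts with the first, second and fourth. A logistic model for a classification variable returns only existing categories, so it cannot produce a value such as 4.08.

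**2. Size if the sentence were applied literally**

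From the documents: 80 completers per arm and a planning odds ratio of 2.607 (SAP section 4). Assumed, because the documents give neither: placebo percentages on scores 1 to 7 of 1/8/21/36/22/10/2 or the mirror image, and 5% to 20% of E2027 scores censored independently of outcome.

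Placebo mean = 0.01×1 + 0.08×2 + 0.21×3 + 0.36×4 + 0.22×5 + 0.10×6 + 0.02×7 = 4.08. The mirror image has mean 8 − 4.08 = 3.92.

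Mechanism: a score of 4.08 ranks worse than every placebo subject scored 4 or lower, which is 1 + 8 + 21 + 36 = 66%, and better than the other 34%. At 3.92 under the mirror distribution these shares swap. A draw from placebo is balanced on average.

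For a censored fraction f, the E2027 arm is (1 − f) × the placebo distribution shifted by the true odds ratio, plus f placed (a) at the unrounded mean as an extra category, (b) at 4, or (c) over the placebo categories. A proportional odds model with treatment as the only covariate was fitted to the expected counts. Odds ratios for improvement:

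| True OR | f | Placebo mean | (a) unrounded mean | (b) rounded to 4 | (c) ordinal draws |
|---|---|---|---|---|---|
| 1 | 5% | 4.08 / 3.92 | 0.95 / 1.05 | 1.01 / 0.99 | 1.00 |
| 1 | 10% | 4.08 / 3.92 | 0.90 / 1.11 | 1.01 / 0.99 | 1.00 |
| 1 | 15% | 4.08 / 3.92 | 0.86 / 1.17 | 1.02 / 0.98 | 1.00 |
| 1 | 20% | 4.08 / 3.92 | 0.82 / 1.23 | 1.03 / 0.97 | 1.00 |
| 2.607 | 15% | 4.08 / 3.92 | 1.89 / 2.63 | 2.32 / 2.22 | 2.24 |

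With true OR 2.607 and mean 4.08, the approximate z under (a) is 2.23 at 15% censored and 1.88 at 20%. Under (c) it is 2.78 and 2.62, before between-imputation variance is added.

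Placebo means away from 4: with an assumed distribution of 0.5/3/13/33/32/15/3.5 (mean 4.52), the share at or below 4 is 49.5%, so an unrounded mean is nearly balanced. At true OR 2.607 and 10% censored, (a) gives 2.34 against 2.36 for (c). The mirror image (mean 3.48) gives 2.32 against 2.36.

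**The case against.** The strongest reply is that the SAP already settles the method. The section says it repeats the primary analysis and adds a reason for missingness, not a new imputation. Under the primary analysis, MNAR scores "will be imputed by ordinal responses observed in the placebo group using a pattern-mixture model approach under MNAR assumption". Table 4 lists control-based pattern imputation as the EMA primary method, and its sensitivity row mentions only the censoring. The protocol (9.7.1.6.1) uses the same mean-response wording in its list of missing-data reasons under MoCA, then applies those reasons to CIBIC-Plus with explicit ordinal imputation. On this view the sentence is a drafting leftover with a cross-reference that leads nowhere.

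Most of this stands. A reader might infer that the SAP has settled on entering the placebo mean into the proportional odds model, so that the odds ratio turns on which side of 4 that mean falls. The documents do not support that: the weight of the text points to ordinal imputation, no placebo mean is given, and the swing needs an unrounded mean close to 4. A reader might also infer that significance would be lost. In the calculation above, z falls below 1.96 only at 20% censored, the top of an assumed range, with the mean just above 4.

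The reply does not remove the contradiction. In the protocol a method does follow the sentence; in this SAP section none does. Table 4 describes the MoCA sensitivity analysis as like the primary, but does not say so for CIBIC-Plus.

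**Conclusion.** The point holds as an internal contradiction in the SAP. The sentence belongs to MoCA, refers to a method that is absent, and conflicts with the ordinal rule stated in two other places and with the aim of its own section.

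The numerical consequence is conditional. A literal reading with an unrounded placebo mean near 4 biases the odds ratio in either direction, from 0.95 or 1.05 at 5% censored to 0.82 or 1.23 at 20% with no drug effect. Rounding a mean that close to 4 keeps it within 0.97 to 1.03, though every censored subject then receives the same score and imputation uncertainty is lost. A mean about midway between two categories also gives little bias. All of this rests on assumed placebo distributions and censoring fractions.

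The success criterion in SAP 5.3.3 uses the co-primary analyses, which are untouched. The effect is confined to one sensitivity analysis for one registration, and the exclusion analysis is available beside it. The sentence should still be corrected before unblinding, because it leaves an analyst a choice that the plan should make.

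**What to change.** In SAP 5.4.1, EMA sensitivity analysis of CIBIC-Plus, replace the words of the mean-response clause ("would be imputed by the mean response in the placebo treatment group as described by the imputation method below") with:

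> *will be set to missing and imputed as ordinal categories by Step 2 of the control-based pattern imputation described for the EMA primary analysis of CIBIC-Plus, analysed with the same proportional odds model and combined with Rubin's rules*

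Keep the mean-imputation sentence for MoCA only. No matching change is needed for CGIC-DLB, because SAP 8.1.4 confines this censoring to the co-primary endpoints.

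The cost is one sentence before unblinding. Step 2 is already planned for the primary analysis, so no new data or method is needed, only further imputation runs.
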